3.1. Type of study

- Three-armed, parallel design randomized comparative trial
- Allocation ratio 1:1:1
- Randomization stratified by the presence or absence of concomitant systemic therapy for uveitis (e.g., oral corticosteroids and/or immunosuppressive drugs)
- Unit of randomization is patient, not eye; if both eyes meet eligibility criteria, both receive the assigned treatment
- Multicenter
- Fixed sample size, 267 (89 per treatment group)
- Anniversary close-out at the 24 week clinic visit
- Reading center graders assessing primary outcome and visual acuity examiners masked to treatment
- Open-label; treating physicians and patients unmasked to treatment (the therapies are different in appearance and have potentially different injection schedules)

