3.3. Trial schema

* Eye(s) meeting trial eligibility criteria receive initial injection of assigned treatment at P01 visit.

† Second injection of assigned treatment permitted at 8 week visit or later for periocular and intravitreal triamcinolone acetonide and at 12 week visit or later for intravitreal dexamethasone when following conditions are met:

- Eye does not meet the improvement definition (a 20% decrease in central subfield thickness of the macula) OR eye has a normal central subfield thickness but has cystoid spaces in the 1 mm central subfield OR ME is worse after initial improvement;
- IOP of <25 mm Hg and treatment with ≤3 IOP-lowering agents;

‡ Eyes demonstrating < 20% reduction or worsening of ME as measured by the central subfield macular thickness on OCT are considered primary treatment non-responders at these time points

§ Macular Edema Ranibizumab v. Intravitreal Anti-inflammatory Therapy (MERIT) Trial is a companion study to POINT (funded by the same grant) for treatment of macular edema persisting after intravitreal triamcinolone therapy. MERIT will begin enrollment approximately 1 year after the initiation of POINT and continue concurrently. POINT participants who meet MERIT eligibility criteria at indicated time points may enroll in MERIT while concurrently completing follow-up in POINT. MERIT will evaluate the relative effectiveness among two regionally-administered alternatives to regional corticosteroid injections, a) intravitreal ranibizumab (Lucentis®, Genentech Inc., San Francisco, CA), and b) intravitreal methotrexate (MTX), with c) the intravitreal dexamethasone (Ozurdex) for the treatment of uveitic macular edema persistent after intravitreal corticosteroids.

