The primary outcome measurement for the POINT Trial is percent change from baseline in retinal thickness at 8 weeks. The primary analysis will be based on the assigned treatment and all randomized individuals will be included in the analysis (intention-to-treat) with additional sensitivity analyses based on treatment received. Individuals will be randomized to treatment groups, i.e., all eligible eyes from an individual will receive the same treatment.

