Power calculations for the primary hypotheses are based upon pair-wise comparisons of the three treatment arms: intravitreal injection of triamcinolone, dexamethasone pellet, and periocular injection of triamcinolone. A Bonferroni correction will be used to adjust for multiple comparisons, i.e. a two-sided type I error rate of $0.05/3 = 0.01667$ will be used to determine statistical significance. The sample sizes needed to provide 90% power for the superiority hypotheses (intravitreal injection or dexamethasone pellet versus periocular injection) and 80% power for the non-inferiority hypothesis (intravitreal injection versus dexamethasone pellet) were computed separately for each comparison and then the maximum sample size was selected. The primary outcome is the change in retinal thickness at the central subfield at 8 weeks. Given the skewness in the distribution of retinal thickness, a log-transformation will be used to analyze the primary outcome^{74, 87}; hence, the comparisons will be represented on a relative scale (i.e. percent of baseline) and transformed to obtain the percent change from baseline. A 20% change in retinal thickness is associated with clinically meaningful changes in visual acuity.⁷⁴ In the MUST Trial, approximately 25% of individuals had bilateral macular edema and the correlation between-eyes was 0.40 for log retinal thickness.^{4, 6} The standard deviation for change in log retinal thickness was approximately 0.33 in the MUST Trial; a conservative estimate since the treatment of macular edema was not standardized and the timing of the assessment, at 6 months after randomization, was not linked to the implementation of treatment for macular edema. Based upon the 6-month OCT evaluation in the MUST Trial, we allowed for a 10% loss to follow-up.

For the first two superiority hypotheses, we evaluated the power to show that each of the treatment methods for intravitreal corticosteroids (triamcinolone injections and dexamethasone pellets) is superior to periocular triamcinolone injections at 8 weeks. In previous studies, treatment with the dexamethasone pellet has resulted in a decrease in retinal thickness of 30%-

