6.2. Statistical methods

The primary analysis will adhere to the intention to treat principle regardless of treatment deviations made either in error or per the best medical judgment of the treating ophthalmologist. Evaluation of continuous outcomes over time (such as log change in retinal thickness or best corrected visual acuity) and binary outcomes over time (such as normal/abnormal IOP) will use a repeated measures analysis with Gaussian or logit links that account for the nested correlations between observations over time and between eyes of the same patient.⁹⁰ A saturated mean model, including visit and visit by treatment interaction terms, will be used. An unstructured covariance matrix will be used to model the within-eye repeated measurements augmented by random effects to induce cross-sectional between-eye associations. Alternatives, including a first-order, auto-regressive process (an AR(1) model) along with a random intercept, will be considered if the unstructured covariance model is unstable. This structure allows for correlation to decrease with increasing time-separation down to a level set by the random intercept.

Significance for superiority hypotheses in POINT will be determined by comparing the p-value of the interaction term for the week 8 visit with 0.01667 (i.e. 0.05/3). Significance for the non-inferiority hypothesis in POINT will be assessed by comparing the upper bound of the 96.7% confidence intervals for estimate of the difference in change in log retinal thickness at 8 weeks, which is estimated by the 8-week interaction term, with the defined non-inferiority boundary of 0.15 on the log scale, which is equivalent to a 10% difference in percent reduction (40% vs 30% reduction) for the two groups.

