The best protection against bias caused by missing data is to prevent it. We will work with coordinators and participants, as we have done in previous trials, to ensure that missing data are infrequent. Regardless, we will perform a variety of sensitivity analyses to determine the potential for bias due missing data. For a crude estimate of the range of potential impact, 'best' and 'worst' case single imputation techniques will be implement. In addition, more sophisticated approaches (e.g. multiple imputation and pattern mixture) will also be used to assess the impact of missing data^{95, 96}. For the principal sensitivity analysis, we will retain all features of the primary analysis other than how missing values for visits beyond the last one with a measured value are handled. As is implicit in the primary analysis where missing data indicators are used (e.g. "." in SAS, "NA" in R), we will treat all missing values as Missing at Random (MAR). We will impute other missing values to generate 10 pseudo-complete records for each such individual by sampling from a joint predictive distribution for the missing data given the observed data. We will use a covariance matrix equal to the estimated covariance matrix from the primary analysis, but will "take control" of the prediction mean. Varying the mean of the predictive distribution allows us to assess the sensitivity of our results to a variety of missing data scenarios. The pattern mixture model approach stratifies participants on their pattern of missing data, estimates stratum-specific parameters and then combines estimates over strata using inverse variance weights. The approach is similar to stratified analysis to adjust for potential confounders and allows for comparison of stratum-specific estimates. We stratify by three patterns: complete data, at least one internal measurement missing, and closeout weight missing (along with any other missingness).

7. Regulatory and ethical issues

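### The pattern-mixture check weights both arms' missingness patterns alike, so it removes arm-differential loss instead of testing it; skipped week-8 OCTs also escape the controlled-mean imputation

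*Combined protocol and SAP*

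**What the plan says.** The primary endpoint is the change in central subfield thickness at 8 weeks (section 3.4). The primary analysis is a repeated-measures model over all visits, and the treatment difference is a single parameter, "which is estimated by the 8-week interaction term" (section 6.2). Close-out is at week 24 (section 3.1), so week 8 is one of the internal visits.

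The last paragraph of section 6.2 lists three kinds of sensitivity analysis for missing data:

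- Best-case and worst-case single imputation, offered as a crude range.
- A principal sensitivity analysis by multiple imputation with a controlled prediction mean. It keeps every feature of the primary analysis "other than how missing values for visits beyond the last one with a measured value are handled".
- A pattern-mixture analysis that "estimates stratum-specific parameters and then combines estimates over strata using inverse variance weights". The plan likens it to a stratified adjustment for confounding. Its strata are: "We stratify by three patterns: complete data, at least one internal measurement missing, and closeout weight missing (along with any other missingness".

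The only figure for missingness is in section 6.1: "Based upon the 6-month OCT evaluation in the MUST Trial, we allowed for a 10% loss to follow-up". No rate is given by arm or for week 8.

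**The concern.** Stratifying with common weights is right for a baseline confounder, because the aim there is to remove an imbalance between arms. A missingness pattern arises after randomisation, and an imbalance in it may be part of what the treatments did. A pattern-mixture estimate of the marginal effect should therefore weight each arm's pattern means by that arm's own pattern proportions. With common weights, the imbalance that the check ought to examine is removed.

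Two further features narrow what these analyses can show about week 8. The internal-missing pattern puts participants without the week-8 OCT together with those who missed only another internal visit. The close-out-missing pattern puts participants lost before week 8 together with those whose week-8 OCT was obtained. Only the complete-data pattern is uniform. In addition, the controlled-mean imputation varies only values after the last measured visit, so a participant who skips week 8 and returns keeps a missing-at-random value there.

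At stake is how a robustness result would be read. A pooled difference near 0 beside a larger primary estimate could be taken as a correction of the primary result when it is the less accurate of the two.

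**Working it through.** **Inputs from the documents.** 89 per arm (section 3.1); SD of log change 0.33 (6.1); non-inferiority margin 0.15 on the log scale and one-sided alpha 0.01667 (6.1, 6.2).

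**The plan's own figures first.** SE of a difference = 0.33 × sqrt(2/89) = 0.0495. Non-inferiority power at a true difference of 0 is 81.7% (stated: 80%). Superiority power at log(0.75) − log(0.60) = 0.223 is 98.3% (stated: 98%). Both reproduce. With the one-sided critical value 2.128, the slack to the margin at an estimated difference of 0 is 0.15 − 2.128 × 0.0495 = 0.15 − 0.1053 = 0.0447.

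**Assumptions, not in the documents.** A share q of each arm is incomplete. Incomplete eyes are 0.30 log units thicker at every visit. There is no treatment difference within a pattern. Half of the incomplete eyes have the week-8 OCT.

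**Algebra.**

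- True arm difference = 0.30 × (q1 − q0).
- Pooled difference = Σ w_k × (mean in arm 1, pattern k − mean in arm 0, pattern k), with the same w_k for both arms. Each bracket is 0, so the sum is 0 for any weights.
- Own-share difference = Σ q_1k × mean_1k − Σ q_0k × mean_0k, which equals the truth when the pattern means are right.

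| Incomplete | Truth | Pooled |
|---|---|---|
| 20% v 5% | 0.30 × 0.15 = 0.045 | about 0 |
| 15% v 5% | 0.30 × 0.10 = 0.030 | about 0 |
| 12% v 8% | 0.30 × 0.04 = 0.012 | about 0 |
| 10% v 10% | 0 | about 0 |

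In 20,000 simulated trials with the three patterns as written (incomplete eyes split equally between internal and close-out, week-8 values only), the pooled result was within 0.0003 of 0 in every row.

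**Against the planned primary model.** A large-sample unstructured repeated-measures fit was run for 20% v 5%. Half of the incomplete eyes skipped week 8 and half skipped another internal visit; within-eye correlation was 0.3 to 0.7.

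| Estimate | Week-8 difference |
|---|---|
| Truth | 0.045 |
| Primary-type model | about 0.039 to 0.044 |
| Within-pattern contrasts (hence any common-weight pool) | near 0, up to 0.01 |
| Own-share weighting | 0.045 |

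The primary-type model is 0.001 to 0.006 short of the truth. The pooled estimate is about 0.045 short, which is 0.045/0.15 = 30% of the margin.

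**Skipped visits in the controlled-mean analysis.** Suppose 10% of one arm lack the week-8 value and the shift under test is 0.30. The full effect on that arm's mean is 0.10 × 0.30 = 0.030. If 0, 50% or 100% of those values are skipped visits followed by a return, the analysis as worded applies 0.030, 0.015 or 0.

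**Where weighting cannot help.** If only the unmeasured values are worse (10% v 2.5% of week-8 values), the truth is 0.30 × (0.10 − 0.025) = 0.0225, while the observed-data and pooled results are both 0. Only a shift parameter can show this.

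**The case against.** **Inverse variance is not the cause.** This stands. With no within-pattern treatment difference, any weights common to both arms give 0. Nor are incomplete patterns materially down-weighted at equal missingness: at 10% v 10% they hold 0.05/0.95 = 5.3% of the eyes with a week-8 OCT and carry 5.3% of the two-pattern weight. The fault is common weights over a post-randomisation pattern.

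**The estimate does use unmeasured values.** A reader might infer that it has no term for them. The documents do not support that: a repeated-measures fit within a pattern predicts them under missing at random. For the same reason it would be wrong to judge the primary analysis by week-8 values alone. That gives 0.30 × (0.10/0.90 − 0.025/0.975) = 0.026 and an apparent gap of 0.019, most of which the planned model recovers.

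**Other analyses cover the ground.** Partly. The shift parameter is already planned, and best/worst-case imputation is not limited to trailing visits, so it reaches skipped week-8 OCTs. But the plan itself calls that range crude, neither method is specified by arm, and the principal one excludes skipped visits.

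**Another reading of the pooling.** If arm means were pooled with separate weights per arm, the cancellation would not occur; with week-8 values only, the observed-data difference would return. The wording allows this, but the comparison with confounder adjustment, and a primary contrast that is a single interaction term, point to pooled differences. The text should say which.

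**No evidence of unequal loss.** This also stands. The trial is open-label ("treating physicians and patients unmasked to treatment") and a second injection is "permitted at 8 week visit or later for periocular and intravitreal triamcinolone acetonide and at 12 week visit or later for intravitreal dexamethasone", so reasons to attend at week 8 could differ by arm. That is an inference. Section 4.2.2 places the second triamcinolone injection after the week-8 OCT, which ties the two together, and section 3.8 schedules OCT at every visit. The documents do not show that the schedule causes differential skipping, and the schedule is not in question here.

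**Stated purpose.** The plan offers the analysis partly for comparing strata. That use is unaffected; the pooled estimate is the problem.

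**Conclusion.** The point holds for the pooled pattern-mixture estimate and, separately, for the reach of the controlled-mean imputation at week 8. The first is structural: common weights remove arm differences in pattern shares whatever the numbers. Its size depends on assumptions that the documents neither supply nor exclude. At 20% v 5% incomplete and 0.30 log units, the pooled result is about 0 against a truth of 0.045, while the primary-type model gives about 0.039 to 0.044. At 12% v 8% the truth is only 0.012, and at equal missingness nothing is lost.

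A reader might infer that the primary result is biased or that the missing-data plan as a whole fails. Neither follows. The decision rule rests on the primary model, whose shortfall in the illustration (at most 0.006) is small beside the 0.0447 slack at an estimated difference of 0. The planned shift and the best/worst-case range remain useful, and no reversal of a conclusion is shown. The change is worth making before analysis because, in these cases, the check lies further from the truth than the estimate it is meant to test.

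**What to change.** 1. Replace inverse-variance pooling. Average each arm's pattern-specific week-8 means over that arm's own pattern proportions, then take the difference between arms. Keep the patient as the resampling unit, as section 6.2 already does for its bootstrap, and state how a bilateral participant with one eye missing is classified.
2. For the week-8 endpoint, define the patterns as week-8 OCT observed, missing with later data, and missing with no later data. The two missing patterns contain no week-8 values, so reweighting alone cannot identify their means. Apply the planned controlled-mean shift to all missing week-8 values, skipped visits included, and vary it separately by arm up to the tipping point for each primary conclusion. For scale, with 10% missing and only the dexamethasone arm shifted, non-inferiority tips at 0.0447/0.10 = 0.447 log units if the estimated difference is 0, and at (0.0447 − 0.02)/0.10 = 0.247 if it is 0.02.
3. Correct the reference to a close-out weight so that it names the close-out OCT measurement. The existing patterns can stay for the 24-week outcomes.

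The cost is SAP wording, some programming and no new data. The interval of this sensitivity analysis widens slightly. In simulation at 20% v 5% with 10 imputations and a fixed shift, the SE was 0.0535, against 0.0524 for observed data and 0.0521 for inverse-variance pooling. Allowing for uncertainty in the shift would widen it further.

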7.1. Recruitment and informed consent procedures

Eligible patients will be recruited from the patient populations seen at and referred to the MUST Research Group clinical centers, the majority of which are in the US and one each is in London, England, UK, Melbourne, Australia, and Montreal, Canada. Typically, patients will be identified in the course of usual clinical practice by the study physicians. When a potentially eligible patient is identified, the study physician and study coordinator will describe the study to and discuss the study with the patient. Patients considering enrollment will be given the consent statement and IRB-approved informational materials and allowed time to decide about joining the study. After patients have time to review materials and discuss enrollment with family members when appropriate, the clinic coordinator or study physician will obtain written informed consent, using a written, local IRB-approved consent document based on a prototype prepared by the CC and approved by the CC's IRB, the JHSPH IRB Office. The trial is registered on www.ClinicalTrials.gov (NCT02374060). Recruitment efforts and eligibility criteria for POINT are subject to review and approval by IRBs and the DSMC.

7.2. IRB/Protection of human subjects

7.2.1. *Potential risks and procedures to minimize risks to participants*

The injection procedures, dosage of medication and treatment algorithm within the study will be consistent with standard clinical treatment, e.g., sterile technique. To minimize risks associated with increased ocular pressure post-injection, patients with uncontrolled ocular hypertension or glaucomatous changes will be excluded from the trial. Patients in the trial will not be exposed to risk beyond what they would be exposed to with standard clinical care for their condition. Adverse events encountered will be managed by the best medical judgment of the treating physician.

7.2.2. *Confidentiality*

Confidentiality of patient data will be maintained in accordance with legal regulations. This includes the storage of protected health information (PHI) in locked cabinets or rooms and limited access to secure data areas by certified study personnel. Name, social security number, address, and other such personal data will be kept solely at the clinical center where the patient receives her/his clinical care. All transmission of data to the Coordinating Center for analysis is done by study ID codes alone. A dataset limited so as to contain a minimal amount of protected health information—that required to make the data useful for accomplishing the purposes of the POINT Trial—may be disclosed, as needed, to collaborating study sites, the NEI, and the FDA. Rarely, for reasons of good clinical practice or legal reasons, data with personal information may need to be reviewed by regulatory bodies such as the IRB, FDA, or DSMB. If such an audit occurs, care will be taken to protect confidentiality of participants. Clinically relevant information from the study may be placed in the patient's medical record. The CC will report serious adverse event data for participants randomized to Ozurdex to Allergan (Irvine CA). Release of protected health information to any other persons or organizations will require additional written consent of the patient affected, except as required by law.

A privacy acknowledgment designed to conform to the specifications of HIPAA regulations and approved by the local governing authorities invested with oversight of HIPAA regulations at each participating site, will be signed by the participant before his/her enrollment in the study. This acknowledgement will be included in the consent form or as a stand-alone document per local institutional requirements.

7.2.3. Inclusion of children

Patients under 18 years of age will not be included; the intravitreal dexamethasone pellet is not approved for use in pediatric patients.

7.2.4. Data and safety monitoring

Treatment effects and safety monitoring will be conducted by a study Data and Safety Monitoring Committee (DSMC). The DSMC will consist mostly of members of the standing DSMC, which monitored the Multicenter Uveitis Steroid Treatment (MUST) Trial and now is monitoring the MUST Follow-up Study. However, the Chair of the MUST DSMC, who is a biostatistician, is unable to serve because of potential conflicts of interest. Hence a new biostatistician has been appointed and the Chair of the DSMC for this protocol will be one of the clinical experts. The committee consists of voting members with expertise in biostatistics, clinical trial design, ophthalmology, and medical ethics who were appointed by NEI and non-voting members (i.e., Study Officers). Initially, the DSMC will meet at least twice a year, once in-person and once by conference call. For each DSMC meeting, data will be summarized in a report prepared by the CC. These reports will include information related to monitoring the safety and effectiveness of the study treatments and will include tables and graphs that summarize baseline, outcome, and adverse event data by treatment assignment, and if indicated, within specific subgroups. Analyses will be included as requested by the DSMC. Pertinent information from outside sources such as a reprint of a recent publication reporting on results of other, related studies will also be included as available. The DSMC report will also include an overall study performance report, designed for monitoring the effectiveness of the participating centers.

The DSMC Safety Officer will be appointed from among the physician voting members of the DSMC, who periodically will review summaries of serious adverse event data prepared by the CC between DSMC meetings to make a determination as to whether the event is unexpected and possibly related to treatment.

8. References

Bibliography

2. Lardenoye CW, van Kooij B, Rothova A. Impact of macular edema on visual acuity in uveitis. *Ophthalmology.* 2006;113(8):1446-9. Epub 2006/08/01. doi: 10.1016/j.ophtha.2006.03.027. PubMed PMID: 16877081.
